Chief Investigator	[name] Email: [contact] Work [contact] [contact]				
Study Co-ordinator	[name] Email: [contact] Work [contact] [contact]				
Sponsor	Greater Manchester Mental Health (GMMH) Contact: [name] Email: [contact] [contact]				
Funder	Greater Manchester Mental Health (GMMH)				
Key Protocol Contributors	 [name] [contact] [name] [name] [contact] [name] [contact] [name] [contact] 				
Committees	Steering Group, chaired by CI Operational Group, chaired by CI PPI Group, chaired by CI				

Study Summary

Study Title	Feasibility study of implementation of an evidence-based creative group psychotherapy for depression (Arts for the Blues) into primary care mental health services					
Short Title	Implementing creative psychotherapy in primary mental health services					
Study Design	Mixed Methods					
Study Participants	Service users with depression					
Planned Size of Sample	24 Total – 8 for each setting					
Follow up duration	3 months					
Planned Study Period	12 months					
Research Question/ Aims	 Research Questions: How can the Arts for the Blues model be implemented into primary care mental health services? How acceptable is the Arts for the Blues model within the services for the participants and therapists? What is the impact of the Arts for the Blues model for participants on depression scores as well as anxiety, wellbeing, and quality of life? The study aims to evaluate the feasibility of implementing the Arts for the Blues into primary care mental health services. 					

Funding and Support in Kind

Funder	Financial and Non Financial Support Given
Greater Manchester Mental Health NHS Foundation Trust	Strategic Research Funding

Role of Study Sponsor and Funder:

The responsibility of study design, conduct, data analysis and interpretation, and dissemination of results lies with the Chief Investigator and Co-Investigators. GMMH will have oversight of monitoring and audit as the project sponsor with support from the research team

Roles and Responsibilities of Study Management Committees/ Groups & Individuals:

Steering Group

The Steering Group will meet 12 times a year, with the following members invited: Chief Investigator (CI), Research Assistant, Clinical Lead for 1Point Bolton, Clinical Lead for Six Degrees Salford and co-applicants.

Operational Group

The Operational Group, consisting of the CI and Research Assistant will meet weekly. The operational group will be responsible for the administration of the project.

Patient and Public Involvement Group

PPI group consulted at design stage

Protocol Contributors:

[name] (NHS Talking Therapies)

[figure not shown]
[name] (Edge Hill University)

[name] (University of Salford)

[name] (Edge Hill University)

Keywords: Arts for the Blues; NHS Talking Therapies; Creative Psychotherapies; Depression; Feasibility study.

Study Flow Chart:

Study Protocol.

Feasibility study of implementation of an evidence-based creative group psychotherapy for depression (Arts for the Blues) into primary care mental health services

1. Background:

According to the World Health Organisation (2021), depression is a condition affecting over 280 million people worldwide and in the UK, depression and anxiety are the most common mental health problems affecting 7.8% of the population (Mental Health Foundation, 2016). Given that depression often remains undiagnosed, it is possible that the size of the problem is much larger than these statistics show.

Currently, National Health Service (NHS) talking therapies (formally Improving Access to Psychological Therapies [IAPT]) is the main provider of evidence-based psychological therapies for adults within the NHS. Whilst Cognitive Behavioural Therapy (CBT) is the main modality offered, other approaches such as 'counselling for depression' are offered in a limited capacity. Even less common is the provision of any arts psychotherapies, i.e. music, drama, art or dance movement psychotherapy. Recent findings identified that about 48% of clients drop out of IAPT (NHS Digital, 2022) indicating that therapies offered in IAPT may not always meet the clients' needs (Martin et al., 2021).

A recent survey by Millard et al. (2021) reported that over 60% of service users and the general public would like to see creative forms of psychological therapies as an option when they contact services. There is evidence for the effectiveness of arts psychotherapies for depression. The Cochrane review by Meekums et al. (2015) and the recent meta-analysis by Karkou et al. (2019), which focused on specific studies in dance movement psychotherapy for depression, along with a similar review in music therapy (Maratos et al., 2011) and art psychotherapy (Uttley et al., 2015) indicate that, despite the limited number of good quality randomised controlled trials, the evidence suggests positive effects for these arts interventions. Similarly, systematic review of arts psychotherapies for older adults (Dunphy et al., 2018) suggests that these positive outcomes can be relevant for all forms of arts psychotherapies across age groups.

More recently and following recommendations from the Medical Research Council (Skivington et al., 2021) on the development and evaluation of complex interventions, we have developed a manualised treatment called **Arts for the Blues** that capitalizes on best practice from CBT, counselling for depression and psychodynamic psychotherapy as well as best practice in arts psychotherapies. Following a synthesis of the evidence (Parsons et al., 2020), we invited public input (Haslam et al., 2019) and contributions from IAPT staff and service users (Karkou et al., 2022) integrating creative ideas (Thurston et al., 2022). We have also delivered the full model in schools (Moula et al., 2020) and at the charity Mind (Omylinska-Thurston et al., in preparation).

2. Rationale:

The model described at Omylinska-Thurston et al. (2020) offers the promise of a useful intervention but further evaluation is needed in adult services since the one group offered at

the charity Mind involved only seven participants and was delivered online due to Covid-19 restrictions.

The evidence for Arts for the Blues for adults for depression has been established in the context of the charity MIND but the study had a small sample size. In this study we aim to translate the findings from MIND to the NHS context in order to build our evidence base and also to see whether this intervention could be implemented in the NHS setting in the future.

3. Theoretical Framework:

Arts for the Blues is a manualised group psychotherapy which utilises best practices from Cognitive Behavioural Therapy (CBT), counselling for depression, psychodynamic psychotherapy and arts psychotherapies. The model offers a structured, evidence-based, group, short-term psychotherapy (Haslan et al., 2019). It follows a pluralistic approach to psychotherapy using creative methods and holds the therapeutic relationship at the heart of the work. There are eight key ingredients which are core components of the intervention model and are regarded as responsible for therapeutic change (Omylinska-Thurston et al., 2020). The model is offered over twelve 90-minute sessions and is comprised of eight key ingredients which are delivered through diverse forms of creative engagement such as visual arts, music, dance and movement, drama and creative writing. The eight key ingredients are as follows:

- Encouraging active engagement
- Learning skills
- Developing relationships
- Expressing emotions
- Processing at a deeper level
- Gaining understanding
- Experimenting with different ways of being
- Integrating useful material

The Intervention will be facilitated by psychotherapists trained in the Arts for the Blues model. It is expected that creative methods will support engagement, enable non-verbal opportunities for recovery and contribute towards the attractiveness, acceptability and value of the Intervention. Ongoing research suggests Arts for the Blues is a useful group intervention, however further evaluation of the model is needed in adult services

4. Research Question / Aims:

This study aims to evaluate the feasibility of implementing the Arts for the Blues into primary care mental health services.

Research Questions:

- (i) How can the Arts for the Blues model be implemented into primary care mental health services?
- (ii) How acceptable is the Arts for the Blues model within the services for the participants and therapists?
- (iii) What is the impact of the Arts for the Blues model for participants on depression scores as well as anxiety, wellbeing, and quality of life?

4.1 Objectives:

- 1. To prepare for the delivery of a creative group psychotherapy Arts for the Blues within primary care mental health services (NHS Talking Therapies, 1Point Bolton and Six Degrees Salford)
- 2. To deliver the Arts for the Blues psychotherapy group (One group per primary care mental health service)
- 3. To evaluate the impact of the Arts for the Blues groups using:
 - a. Qualitative methods (understanding participant and therapist views on helpful and unhelpful aspects of the Arts for the Blues model)
 - b. Quantitative measures (Depression, anxiety and wellbeing scores)

4.2 Outcome:

Our intention is to integrate Arts for the Blues into primary care mental health services and to provide an alternative treatment option for adults with depression in Greater Manchester. The study will help towards building the evidence base for this approach, preparing for a Randomised Clinical Trial (RCT) in the future. The overall aim is to propose changes on a policy level for inclusion of creative approaches into national provision of therapies for depression.

5. Study Design and Methods of Data Collection and Data Analysis:

We will adopt an overall case study design (Yin, 2017) that will include pre- and post-measures in a mixed methods approach (Creswell, 2014). The mixed methods design will collect both quantitative and qualitative data.

Quantitative

Quantitative data will be collected pre and post intervention, weekly, in week 6 of the intervention and 3 months post intervention. All quantitative data will be analysed and presented using descriptive statistics. Quantitative data will be collected using:

- Patient Health Questionnaire (PHQ-9) (Kroenke et al., 2001) (collected pre and post intervention, weekly and 3 months post intervention).
- Generalised Anxiety Disorder assessment (GAD-7) (Spitzer et al., 2006) (collected pre and post intervention, weekly and 3 months post intervention).
- Work and Social Adjustment Scale (WSAS) (Mundt et al., 2002) (collected pre and post intervention, weekly and three months post intervention).
- WHO's Five Well-Being Index (WHO-5) (Topp et al., 2013) (collected pre and post intervention and 3 months post intervention).
- Goal Based Outcomes (GBO) (Law & Jacob, 2013) (collected pre and post intervention, midway (in week 6 of the intervention) and 3 months post intervention).
- Group Session Rating Scale (GSRS) (Quirk et al., 2013) (Collected weekly).

PHQ-9 and GAD-7 are relevant measures for adults with depression and anxiety and are standardised measures used within NHS Talking Therapies services. These measures are extensively used in the NHS, allowing for findings to become comparable with routine psychological provision and outcomes.

WSAS is used routinely in NHS settings and assess the impact of an individual's mental health on their ability to function across various settings (e.g. work, home, social)

WHO-5 is a brief measure that is quick to complete and relevant for the intervention. Whilst PHQ-9 and GAD-7 will measure reduction of difficulties, WHO-5 will capture strengths.

The GBO measure will be used to personalise the intervention and identify any goalorientated changes over time. A weekly GSRS (Quirk et al., 2013) will be completed to identify participants' experience of group therapy and therapeutic progression.

The Arts for the Blues research team will only have access to anonymised data which will be used for analysis.

Qualitative

Qualitative data will be collected post-intervention and will be subjected to thematic analysis (Clarke & Braun, 2013). Qualitative data will be collected using:

- Evaluation forms completed by participants
- Adherence forms completed by therapists
- Focus groups Online or in-person. Facilitated by a member of the research team or therapist and will be audibly recorded

Focus groups will be transcribed and analysed by a research assistant using a password protected computer. Once the transcriptions have been completed, the recordings will be deleted. Any paper-based data will be uploaded to the GMMH secure network drive and the hard copy will be destroyed.

Adherence Forms will be completed by the Arts for the Blues therapist which comprise of quantitative and quantitative data. The Adherence Form requires the therapist to evaluate the Arts for the Blues model each week using numerical scales with space for additional comments on the Arts for the Blues model.

6. Study Setting:

This study is a multicentre study. The following centres will be participating in the study:

NHS Talking Therapies

Greater Manchester Mental Health NHS Foundation Trust Prestwich Hospital [name]

1Point Bolton

[name]

Six Degrees Salford

[name]

The study will take place either in-person or online. If in-person, the sessions will take place at the above locations where the participant has been recruited from. In-person groups from GMMH will take place at the Booth Centre:

[name]

Risk assessments will be completed for in-person locations. If online, the sessions will take place on MS Teams, with the link being sent directly to participants via email.

7. Sample and Recruitment:

7.1 Eligibility Criteria:

Participants will be screened against eligibility criteria during the screening and their eligibility will be confirmed at the Arts for the Blues meeting.

7.1.1 Inclusion Criteria:

- aged 18 years or over.
- must have depression or symptoms of depression (assessed by PHQ9 >5).
- is interested and willing to take part in group work.
- is interested and willing to take part in the creative interventions.
- is able to communicate in English at a basic level without the need for an interpreter.

7.1.2 Exclusion Criteria:

- too physically unwell to attend the intervention.
- currently at risk of harming self and/or others.
- regularly misusing alcohol or other illegal substances which would make engaging in the group difficult.
- experiencing psychotic episodes which would make engaging in the group difficult.
- is severely psychologically distressed and/or who is presenting any condition which could interfere with regular attendance, such as significant dissociation, severe social anxiety, paranoia, difficulties in comprehension, difficulties in emotional regulation, severe personality disorder, severe depression.
- Is currently participating in other research

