Appendix 2 – Schedule of Procedures

	Screening	Baseline	Visit 1	Visit 2	Visit 3	Visit 4	Visit 5	Visit 6	Visit 7	Visit 8	Visit 9	Visit 10	Visit 11	Visit 12	Visit 13	Visit 14
Initial Assessment / Screening	X															
Arts for the Blues meeting		X														
Consent Process		Х	Х													
Intervention			Х	X	X	X	Х	X	Х	X	X	X	Х	Х		
Questionnaires		Х	Х	X	X	X	Х	X	Х	X	X	X	Х	Х		X
Evaluation forms														X		
Focus Groups															Х	

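### Participants' qualitative views on acceptability are scheduled only at or after the last session, with no provision for the views, reasons or end-of-treatment scores of people who stop earlier

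*Protocol*

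**What the plan says.** Research question (ii) in Section 4 reads "How acceptable is the Arts for the Blues model within the services for the participants and therapists", and objective 3a in Section 4.1 asks for participants' and therapists' views on what helped and what did not. On timing, Section 5 (Qualitative) states: "Qualitative data will be collected post-intervention and will be subjected to thematic analysis". In Appendix 2 the row "Evaluation forms" has a single mark, at Visit 12, which is the last intervention session. The focus group row also has a single mark, at Visit 13. Questionnaires are marked at baseline, at each of Visits 1 to 12, and at Visit 14.

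Section 5 (Quantitative) sets the timing of each scale:

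- PHQ-9 and GAD-7: "collected pre and post intervention, weekly and 3 months post intervention". WSAS follows the same pattern.
- WHO-5: "collected pre and post intervention and 3 months post intervention".
- GBO: before and after the intervention, then "midway (in week 6 of the intervention) and 3 months post intervention".
- GSRS: weekly; it "will be completed to identify participants' experience of group therapy and therapeutic progression".

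Therapists also rate the model each week on the adherence form, with room for comments. Section 7.3 lets participants withdraw at any time. The Background (Section 1) reports that "about 48% of clients drop out of IAPT" and reads this as a hint that the therapies offered do not suit everyone.

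**The concern.** The evaluation form and the focus group are the only listed sources in which participants describe the therapy in their own words. Both come at or after the end. Someone who stops at session 4 has no scheduled occasion to say what was unhelpful or why they stopped. Their end-of-treatment questionnaire is tied to a session they will not attend.

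By the protocol's own reasoning in the Background, leaving is itself evidence about acceptability. A schedule that gathers accounts mainly from people who stayed leans the answer to question (ii) towards the favourable side. Section 4.2 says that the study is to prepare for a randomised trial, so the lean would carry into that design. Analysis cannot recover views that were never collected, so this is a matter for the protocol and cannot be left to a later analysis plan.

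**Working it through.** **Who is recruited.** Section 7.2.1 gives about 8 participants in each of three services: 3 × 8 = 24, which agrees with the stated total. There is no power calculation to reproduce, and all quantitative analysis is descriptive.

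**What a person who stops before Visit 12 would contribute under the schedule as written.**

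| Source | Timing in the protocol | From an early leaver |
|---|---|---|
| Evaluation form | Visit 12 | Not provided for |
| Focus group | Visit 13 | No statement either way |
| Reason for leaving | Not mentioned | Not provided for |
| GSRS | Weekly | Up to last session attended |
| PHQ-9, GAD-7, WSAS | Baseline, weekly, end, 3 months | Up to last session; no out-of-session route at Visit 12 |
| GBO | Before, week 6, end, 3 months | Week 6 if still attending |
| WHO-5 | Before, end, 3 months | Nothing between baseline and the end |
| Therapist adherence form | Weekly | Unaffected, but not the participant's view |

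The gap is therefore specific: the qualitative view, the reason for leaving, and the end-of-treatment measure. Of the scales taken at baseline and end, only WHO-5 has no value in between.

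**How many people this could concern.** The protocol states no drop-out assumption for this study. The 48% is its background figure for IAPT services; 10%, 20% and 30% are my assumptions, added to show a range. With drop-out proportion d, expected leavers = 24 × d, and per group = 8 × d.

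| d | Expected leavers of 24 | Per group of 8 | Chance of no leaver, (1 − d)^24 |
|---|---|---|---|
| 0.10 | 2.4 | 0.8 | 0.080 |
| 0.20 | 4.8 | 1.6 | 0.005 |
| 0.30 | 7.2 | 2.4 | 0.0002 |
| 0.48 | 11.5 | 3.8 | below 0.0001 |

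The last column assumes that people leave independently of one another. That is a simplification in a therapy group, where departures may cluster. Even so, some leavers should be expected at the lowest rate considered.

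**The case against.** **Leavers do contribute data.** A reader might infer from the schedule that early leavers are not heard at all and have no outcome scores. The documents do not support this. The GSRS is completed weekly precisely to capture experience of the group, and three symptom and functioning scales are also weekly. Therapists, who are part of question (ii), report every week. This stands, and it narrows the point. It does not remove it: a rating given while still attending cannot say why the person later stopped, and the therapist's form is not the participant's account.

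**Silence is not exclusion.** Appendix 2 gives timing, not an attendance condition. Nothing bars someone who stopped the sessions from the focus group or from the questionnaires at Visits 12 and 14. Consent under Section 7.3.2 covers the intervention, questionnaires and focus groups, and the focus group may be held online. The evaluation form, the focus group question schedule and the site schedules are separate documents listed in Appendix 1 and not shown. It is fair to say only that this protocol makes no provision for leavers, not that it shuts them out.

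**The 48% is not this study's rate.** It describes IAPT generally. Participants here must be willing to do creative group work, and their ability to attend is discussed beforehand. The figure serves as the upper end of an assumed range and nothing more.

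**No biased percentage can be calculated.** A reader might want to express the bias as an inflated acceptability rate. The protocol plans thematic analysis and defines no such rate or threshold, so any figure of that kind would rest entirely on invented inputs.

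**It is a small descriptive study with limited funding.** True, and the remedy should be light. But acceptability is one of its three research questions, and the forms needed already exist.

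**Conclusion.** The point holds in a limited form. As written, participants' qualitative views are collected only at Visits 12 and 13. No reason for leaving is recorded, and no out-of-session end-of-treatment measure is provided for people who stop earlier. The findings on acceptability would lean towards completers.

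At an assumed drop-out of 10% to 48%, about 2 to 12 of 24 participants would be affected. This takes all 24 as starters and assumes that no leaver is contacted under documents not shown. The direction of the bias, towards a favourable answer, rests on leavers being on average less satisfied. The Background section's reading of drop-out makes that plausible, but it is not established for this therapy. The size of the bias cannot be stated. The weekly scales are not compromised up to the last session attended, and the descriptive design otherwise stands.

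**What to change.** Amend Section 5 and Appendix 2 as follows:

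1. Offer the existing evaluation form, with one added question on the reason for stopping, to everyone who attended at least one session, at the point of leaving or at week 12.
2. Route this contact through the service's Arts for the Blues therapist or the CI. Under Section 8.5 the CI is the only member of the research team with access to personal data, so the research assistant could not make the contact.
3. Offer the Visit 12 questionnaires outside the session, within a stated window, to those who stopped or missed it.
4. State that people who stopped may join the focus group or comment in writing.
5. Report acceptability with all starters as the denominator, together with the number who responded and the reasons for leaving. Separate themes for leavers are not advised: at 20% drop-out there would be about 5 in total, or 1 to 2 per group, too few for themes and a risk to anonymity.
6. Say in the consent form that this contact is optional.

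The cost is an amendment, one extra question, a short consent addition and a few contacts per service. Some leavers will not reply; the response count will then show how far the conclusion reaches. Sample size and treatment are unchanged.

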8.5 Data Protection and Patient Confidentiality

Of the research team, only the CI will have access to participant's personal data and key to pseudonyms, this will be stored separately from the research data to preserve anonymity. The relevant primary care mental health services will have access to personal data as is routine practice. Only anonymised data will be shared with the research team.

The research team who will transcribe the focus groups and assist with data analysis will sign confidentiality agreements and research passports prior to accessing any participant data. They will adhere to these arrangements with particular regard to confidentiality and safeguarding of any personal data, including being mindful of Data Protection Act (2018) and GDPR (2018) requirements, as well as possible Freedom of Information (2000) requests and procedures.

Confidentiality will be maintained as per UKCP (United Kingdom Council for Psychotherapy), BACP (British Association for Counselling and Psychotherapy) and BPS (British Psychological Society) codes of Ethics. This includes protecting sensitive and personally identifiable data pre, during and post intervention and that policy on breaches of confidentiality is made clear in advance to the participants. There may be occasions when confidentiality may have to be breached to the appropriate authorities due to risks of harm to self or others, these instances are:

- 1. Disclosure that requires safeguarding referral,
- 2. Disclosure that highlights risk of harm to the participant(s) or others,
- 3. Disclosure of serious criminal activity.

The above instances are outlined in the PIS and consent form. All concerns will follow a staged process of consultation and reporting and will be addressed according to the relevant mental health service's safeguarding policies and protocols which will be addressed by the designated safeguarding lead in each of the settings.

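### The protocol lets the therapist who delivered a group also lead its focus group, which favours positive answers on acceptability

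*Protocol*

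**What the plan says.** Section 5 (Qualitative) lists three sources collected after the intervention: participant evaluation forms, therapist adherence forms and focus groups. The focus groups may be online or in person and are "Facilitated by a member of the research team or therapist and will be audibly recorded". No criterion for choosing between the two facilitators is given, and no therapist is excluded.

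The focus groups serve two stated purposes. Research question (ii) in section 4 asks: "How acceptable is the Arts for the Blues model within the services for the participants and therapists". Objective 3a in section 4.1 describes the qualitative work as "understanding participant and therapist views on helpful and unhelpful aspects of the Arts for the Blues model".

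On delivery, section 3 states: "The Intervention will be facilitated by psychotherapists trained in the Arts for the Blues model". Section 4.1 plans "One group per primary care mental health service". Sections 7.3 and 7.3.2 have the service's Arts for the Blues Therapist hold the pre-intervention meeting, at which consent is obtained, eligibility is settled and baseline measures are taken.

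**The concern.** Acceptability data are useful only if participants feel able to say what did not work. The facilitator rule allows that question to be put by the person who delivered the sessions. Section 3 says the model "holds the therapeutic relationship at the heart of the work", so a participant would be asked to criticise someone with whom they have a working therapeutic bond. Unfavourable comments about the therapist, the group or the method are the ones most likely to be softened or withheld.

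At stake is the answer to research question (ii). Section 4.2 intends the study to prepare for a randomised trial and to support policy change, so an over-favourable account of acceptability would carry into both. The depression, anxiety and wellbeing scores do not depend on who leads the focus groups.

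**Working it through.** No arithmetic applies. The point depends on no sample size, effect or error rate, and the document gives no figure to reproduce. The check is whether the text permits the problem and whether anything else in it prevents the problem.

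1. **Can the facilitator be the delivering therapist?** Section 5 says only therapist, without qualification. With one group per service, and with the Arts for the Blues Therapist in each service also running the consent and baseline meeting, the participants' own therapist is a natural reading. It is not the only one: a therapist from another service would also satisfy the sentence. The text permits the problem but does not require it.

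2. **Does the purpose need critical answers?** Yes. Objective 3a asks explicitly for unhelpful aspects.

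3. **Do other participant-level sources cover the gap?** Only in part.
   - Evaluation forms: Appendix 2 places them at Visit 12, which is also an intervention session. The Protocol does not say whether the therapist sees them.
   - Group Session Rating Scale: completed weekly and intended to capture the experience of group therapy, but it is a rating scale, not an open account.
   - Adherence forms: completed by the therapist, so they address the therapist half of question (ii).

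4. **Can later steps correct it?** No. Section 5 gives transcription and thematic analysis to a research assistant. That separates analysis from delivery, but does not change what is said in the room.

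5. **Does the timing help?** No. In Appendix 2 the focus group is Visit 13 and the last questionnaires are Visit 14. Section 10 places onward referral or discharge after study completion. Participants would speak while their next step is still open. The Protocol does not say who decides it.

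6. **Is a less exposed facilitator already available?** Yes. The same sentence in section 5 allows a member of the research team.

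The permission is therefore real and no stated safeguard offsets it. The direction of bias is towards acceptability. No size can be attached: the document has nothing from which to estimate it, and it gives one focus-group visit in the schedule without stating how many focus groups there are or whether they are held by service.

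**The case against.** The strongest reply is that this is a small descriptive feasibility study, therapist facilitation is only an option, and criticism has other outlets in the evaluation forms and weekly ratings. The question schedule, evaluation form and information sheets listed in Appendix 1 are not shown and may say who facilitates or how criticism is invited. All of that is fair and keeps the point modest. It does not justify leaving the permission unrestricted, because a question schedule can fix what is asked but not who asks it.

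Two practical objections also stand. Section 8.1 relies on therapists to notice and respond to distress, so excluding the delivering therapist affects that provision. And a research-team facilitator is not fully independent: section 1 says the team developed the model. The change reduces the bias without removing it.

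A reader might infer more than the text supports:

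- **That the data-access wording pushes facilitation towards the therapist.** Section 5 (Quantitative) says "The Arts for the Blues research team will only have access to anonymised data which will be used for analysis", and section 8.5 says "Only anonymised data will be shared with the research team". Read alone, these could seem to keep the team away from recordings. But section 5 names a research-team facilitator and gives transcription to a research assistant, and section 8.5 provides for team members who transcribe to sign confidentiality agreements. The wording is at most loose and could be tidied separately.
- **That the focus groups are the principal source for question (ii).** Section 5 does not rank its sources.
- **That all three services would have a therapist-led focus group.** The number of focus groups is not given.
- **That comparison between services would be confounded by facilitator.** The document specifies a case study design but plans no such comparison.

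**Conclusion.** The point holds as a correctable weakness in data collection. The facilitator sentence in section 5 permits the delivering therapist to lead the discussion in which participants are asked what was unhelpful, and nothing else in the Protocol prevents it. The expected effect is under-reporting of negative views on research question (ii). Its magnitude is unknown.

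This rests on two assumptions: that therapist can include the group's own therapist, which the text allows but does not say, and that people are less willing to criticise a therapy to the person who provided it. The unseen appendix documents could narrow the first. The change is worth making because it costs little, but the weakness does not undermine the study as a whole.

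**What to change.** Replace the facilitator sentence in section 5 with wording such as: *Each focus group will be led by a research-team member who did not deliver the intervention to that group; the delivering therapist will neither lead nor attend.*

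In addition:

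- Report the facilitator's role for each focus group.
- State as a limitation that the research team developed the model, so its facilitator is not a neutral party.
- Reconcile the new sentence with the distress provisions in section 8.1, which currently rest on the therapists. How distress is handled in these sessions is for the study team to settle.

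No new role is needed, because the research-team facilitator is already named. The cost is some research-team time, in a study that section 7.2.1 describes as having limited funding, and slightly less scheduling flexibility.
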